8.3.4. Regulatory Reporting Requirements for Serious Adverse Events

The sponsor assumes responsibility for appropriate reporting of AEs to the regulatory authorities. The sponsor will also report to the investigator (and the head of the investigational institute where required) all suspected unexpected serious adverse reactions (SUSARs).

The investigator (or sponsor where required) must report SUSARs to the appropriate IEC/IRB that approved the protocol unless otherwise required and documented by the IEC/IRB. A SUSAR will be reported to regulatory authorities unblinded. Participating investigators and IEC/IRB will receive a blinded SUSAR summary, unless otherwise specified.

8.3.5. Pregnancy

All initial reports of pregnancy in participants or partners of male participants must be reported to the sponsor by the study site personnel within 24 hours of their knowledge of the event using the appropriate pregnancy notification form. Abnormal pregnancy outcomes (eg, spontaneous abortion, fetal death, stillbirth, congenital anomalies, ectopic pregnancy) are considered SAEs and must be reported using an SAE reporting form.

Any participant who becomes pregnant during the study may continue study vaccination if the investigator considers that the potential benefits outweigh any potential risks to the mother and fetus and is allowed by local regulations.

Follow-up information regarding the outcome of the pregnancy and any postnatal sequelae in the infant will be required.

8.3.6. Adverse Events of Special Interest

AESIs are significant AEs that are judged to be of special interest because of clinical importance, known or suspected class effects, or based on nonclinical signals. Adverse events of special interest will be carefully monitored during the study by the sponsor.

Suspected AESIs must be reported to the sponsor within 24 hours of awareness irrespective of seriousness (ie, serious and non-serious AEs) or causality following the procedure described above for SAEs.

At baseline, safety blood samples will be collected. Whole blood samples will be used for a complete blood counts (CBC), including platelet count (as part of a complete blood count), in a local laboratory or substitute for local laboratory, depending on local feasibility towards turnaround time of sample processing.

Serum and plasma samples will be collected and stored for potential future coagulation-related testing in a central laboratory if the participant experiences an AESI (see Section 10.2, [Appendix 2](#)).

Specific requirements for the AESI are described below.

8.3.6.1. Thrombosis with Thrombocytopenia Syndrome

As described in Section 2.3.1, TTS has been observed very rarely following vaccination with Ad26.COV2.S and is considered to be an AESI in this study. TTS is a syndrome characterized by a combination of both a thrombotic event and thrombocytopenia ([American Society of Hematology 2021](#); [Brighton Collaboration 2021](#)).

Because this syndrome is rare and not completely understood, all cases of thrombosis and/or thrombocytopenia will be considered a suspected case of TTS until further adjudication can be performed. An AESI Adjudication Committee with appropriate expertise will be established to evaluate each suspected AESI and determine whether it is a case of TTS. The investigator shall be responsible for reporting any suspected AESI of TTS using the SAE form and the form detailed in Section 10.8, [Appendix 8](#).

A suspected TTS case is defined as:

- Thrombotic events: any thrombotic or thromboembolic event as detailed in Section 10.9, [Appendix 9](#)
- Thrombocytopenia, defined as platelet count below 150,000/ μ L ([Brighton Collaboration 2021](#)) post-vaccination

Symptoms, signs, or conditions suggestive of a thrombotic event should be recorded and reported as a suspected AESI even if the final or definitive diagnosis has not yet been determined, and alternative diagnoses have not yet been eliminated or shown to be less likely. Follow-up information and final diagnoses, if applicable, should be submitted to the sponsor as soon as feasible.

In the event of post-vaccination thrombocytopenia, study site personnel should report the absolute value for the platelet count and the reference range for the laboratory test used in the eCRF. In the event of thrombocytopenia post study vaccination, thrombotic events should be excluded (through laboratory tests or imaging).

For either a thrombotic event or thrombocytopenia, testing for anti-PF4 should be performed at the central laboratory or substitute local laboratory; repeat testing may be requested for confirmation upon sponsor discretion.

Suspected AESIs will require enhanced data collection and evaluation (see Section 1.3.2). Every effort should be made to report as much information as possible about the AESI to the sponsor in a reasonable timeframe

If an event meets the criteria for an SAE (Section 10.4.1), it should be reported using the same process as for other SAEs.

The form detailed in Section 10.8, Appendix 8 is intended as a guide for assessment of the AESIs to facilitate diagnosis and determine treatment options. If the investigator is not the treating physician, every effort should be made to collect the information requested in the form from the treating physician and enter the available information in the eCRF.

9. STATISTICAL CONSIDERATIONS

Statistical analysis will be done by the sponsor or under the authority of the sponsor. A general description of the statistical methods to be used to analyze the efficacy and safety data is outlined below. Specific details will be provided in the SAP.

9.1. Statistical Hypotheses

The study is successful if the below objectives are demonstrated:

- NI of the humoral immune response as measured by the HI assay after concomitant administration of Ad26.COV2.S vaccine and a seasonal *standard-dose* influenza vaccine versus the administration of a seasonal quadrivalent *standard-dose* influenza vaccine alone, 28 days after the administration of a seasonal influenza vaccine.

AND

- NI of the concomitant administration of Ad26.COV2.S vaccine and a seasonal quadrivalent *standard-dose* influenza vaccine versus the administration of Ad26.COV2.S vaccine alone, 28 days after the administration of Ad26.COV2.S vaccine, in terms of humoral immune response (ELISA)

Therefore, the following CIs will be calculated:

- The 2-sided 95% CIs for the difference in log-transformed HI antibody titers against each of the 4 seasonal influenza vaccine strains at 28 days after the administration of the quadrivalent seasonal influenza vaccine between the Control and the CoAd group, and

- The 2-sided 95% CIs for the difference in log-transformed ELISA titers at 28 days after the administration of Ad26.COV2.S vaccine between the Control and the CoAd group

Only if the upper bound of the 2-sided 95% CI for the GMT ratio (Control group/CoAd group) of the HI antibody titer for each of the 4 vaccine strains and for GMC for ELISA lies below 1.5, NI of co-administration versus separate administration will be concluded for both vaccines (seasonal influenza vaccine and Ad26.COV2.S vaccine). If 1 or more confidence limits for the GMT/GMC ratio exceed 1.5, NI cannot be concluded.

The primary analysis will be performed when all participants have completed the 28 days after the second study vaccination visit or discontinued earlier. No interim analyses will be performed.

For the high-dose groups, no formal hypothesis testing is planned.

No formal statistical testing of safety data is planned. Safety data will be analyzed descriptively by vaccine group.

9.2. Sample Size Determination

Sample size calculations are performed under the following assumptions:

- no effect of co-administration of Ad26.COV2.S vaccine and seasonal influenza vaccine on the immune response against influenza as measured by HI antibody titers against the 4 influenza vaccine strains at 28 days after the administration of seasonal influenza vaccine
- the use of Afluria Quadrivalent for *standard-dose* (adults ≥ 18 to < 64 years of age and older adults ≥ 65 years of age)
- a standard deviation of 0.53 for the *standard-dose* at the \log_{10} scale for HI antibody titers against the 4 influenza vaccine strains at 28 days after the administration of seasonal influenza vaccine (with or without Ad26.COV2.S)
- no effect of co-administration of Ad26.COV2.S vaccine and seasonal influenza vaccine on the immune response against SARS-CoV-2 as measured by S-ELISA at 28 days after the administration of Ad26.COV2.S vaccine
- a standard deviation of 0.50 at the \log_{10} scale for S-ELISA at 28 days after the administration of Ad26.COV2.S vaccine (with or without seasonal influenza vaccine)
- a NI margin of 1.5
- 2-sided α of 5%

A total of approximately 305 (*standard-dose*) participants per group (total N 610) who have completed a primary COVID-19 vaccine series are needed to have 97.45% power to show NI in HI antibody titers for 1 influenza vaccine strain.

The sample size accounts for exclusions from the per protocol set (see Section 9.3), drop-outs and missing samples.

With this sample size, the overall power to show NI in HI antibody titers against each of the 4 influenza vaccine strains at 28 days after the administration of seasonal influenza vaccine as well as NI in S-ELISA at 28 days after the administration of Ad26.COV2.S vaccine is at least 90%.

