1. PROTOCOL SUMMARY

1.1. Synopsis

A Randomized, Double-blind, Phase 3 Study to Evaluate Safety, Reactogenicity, and Immunogenicity of Co-administration of Ad26.COV2.S and Influenza Vaccines in Healthy Adults 18 Years of Age and Older.

Ad26.COV2.S (also known as VAC31518, JNJ-78436735) is a monovalent vaccine composed of a recombinant, replication-incompetent adenovirus type 26 (Ad26) vector, constructed to encode the Spike (S) protein derived from a SARS-CoV-2 clinical isolate (Wuhan, 2019, whole-genome sequence NC 045512, referred to as the original strain), stabilized in its prefusion conformation.

The study aims to assess the safety, reactogenicity, and immunogenicity of the Ad26.COV2.S vaccine co-administered with a quadrivalent *standard-dose* or *high-dose* seasonal influenza vaccine compared to administration of each vaccine separately to explore whether Ad26.COV2.S and the influenza vaccines can be administered concomitantly.

The primary objective (for the NI assessment) will be evaluated in approximately 610 participants aged 18 and above who have completed a primary COVID-19 vaccine series, the co-administration of the Ad26.COV2.S and the seasonal quadrivalent *standard-dose* influenza vaccine. In a cohort of participants aged 65 and above, the co-administration of the Ad26.COV2.S and the seasonal quadrivalent *high-dose* influenza vaccine will be assessed descriptively. In another cohort of COVID-19 vaccine-naïve individuals, immune responses will be evaluated descriptively.

OBJECTIVES AND ENDPOINTS

Objectives	Endpoints
Primary	
To demonstrate the non-inferiority (NI) of the humoral immune response of the 4 influenza vaccine strains after concomitant administration of the Ad26.COV2.S vaccine and a seasonal quadrivalent standard-dose influenza vaccine versus the administration of a seasonal quadrivalent standard-dose influenza vaccine administered alone.	
 Antibody hemagglutination inhibition (HI) titers as measured by hemagglutinin inhibition (HAI) assay titers (geometric mean titers [GMTs]) against each of the 4 influenza vaccine strains, 28 days after the administration of a seasonal quadrivalent standard-dose influenza vaccine 
Success criteria for NI
 
 the upper bound of the 2-sided 95% confidence interval (CI) for the geometric mean titer (GMT) ratio (Control group/co-administration [CoAd] group) lies below 1.5

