### 3. SAMPLE SIZE DETERMINATION

Sample size calculations are performed under the following assumptions:

- no effect of coadministration of Ad26.COV2.S vaccine and seasonal influenza vaccine on the immune response against influenza as measured by HI antibody titers against the 4 influenza vaccine strains at 28 days after the administration of seasonal influenza vaccine
- the use of Afluria Quadrivalent for *standard-dose* (adults  $\geq 18$  to  $<64$  years of age and older adults  $\geq 65$  years of age)
- a standard deviation of between 0.53 for the *standard-dose* at the  $\log_{10}$  scale for HI antibody titers against the 4 influenza vaccine strains at 28 days after the administration of seasonal influenza vaccine (with or without Ad26.COV2.S)
- no effect of coadministration of Ad26.COV2.S vaccine and seasonal influenza vaccine on the immune response against SARS-CoV-2 as measured by S-ELISA at 28 days after the administration of Ad26.COV2.S vaccine
- a standard deviation of 0.50 at the  $\log_{10}$  scale for S-ELISA at 28 days after the administration of Ad26.COV2.S vaccine (with or without seasonal influenza vaccine)
- Log transformed ( $\log_{10}$  scale) immune response data are normally distributed
- a non-inferiority margin of 1.5
- 2-sided  $\alpha$  of 5%

A total of approximately 305 (*standard-dose*) participants per group are needed to have 97.45% power to show non-inferiority in HI antibody titers for each influenza vaccine strain.

The sample size accounts for exclusions from the per protocol set, drop-outs and missing samples resulting in a total sample size up to approximately 610 participants who have completed a primary COVID-19 vaccine series. The N margin was  $\sim 10\%$  ( $\sim 30$  per group).

With this sample size, the overall power to show NI in HI antibody titers against each of the 4 influenza vaccine strains at 28 days after the administration of seasonal influenza vaccine as well as NI in S-ELISA at 28 days after the administration of Ad26.COV2.S vaccine is at least 90%.

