### 4. POPULATIONS (ANALYSIS SETS) FOR ANALYSIS

Analysis Sets	Description
All screened participants (ALL)	The “all screened participants” set includes all participants that were screened, regardless of whether they were enrolled and/or randomized.

Analysis Sets	Description
All randomized participants (ALL RANDOMIZED)	The “all randomized participants” set includes all participants that were randomized to one of the treatment groups.
Full Analysis Set (FAS)	The full analysis set (FAS) includes all participants with a vaccine administration documented.
Per-protocol Influenza Immunogenicity (PPII) Set	
Per Protocol Influenza Immunogenicity (PPII) Set: All randomized participants who received Ad26.COV2.S vaccine in combination with a seasonal influenza vaccine for the coadministration group and those who received a seasonal influenza vaccine alone for the control group, for whom immunogenicity data are available for at least one of the influenza strains in the vaccine.
 
PPII set will include participants who have received a complete primary vaccination with an authorized/licensed COVID-19 vaccine as well as COVID-19 vaccine-naïve participants.
 
Samples taken after (but not before) a participant experienced a confirmed major protocol deviation expected to impact the immunogenicity outcomes will be excluded from the PPII analysis.
 
The primary analysis set for analyses related to influenza immunogenicity is the PPII Set. As a sensitivity analysis, key tables may also be based on the FAS.

Per-Protocol SARS-CoV-2 Immunogenicity (PPSI) Set	
The per protocol SARS-CoV-2 Immunogenicity Set (PPSI) will include all randomized participants who received Ad26.COV2.S vaccine in combination with seasonal influenza vaccine for the co-administration group and Ad26.COV2.S vaccine alone for the control group, and for whom immunogenicity data are available.
 
PPSI set will be restricted to participants who have received a complete primary vaccination with an authorized/licensed COVID-19 vaccine.
 
N seronegative participants at day 1 that became N serology positive during the study will be excluded for analyses of future timepoints.
 
Participants with positive molecular test for SARS-CoV-2 will also be excluded from future timepoints.
 
Samples taken after a participant meets the criteria for a major protocol deviation expected to impact the immunogenicity outcomes will be excluded from the PPSI analysis.

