#### **5.3.2. Analysis Methods**

The NI immunogenicity objectives will be assessed in PPII and PPSI analysis sets by calculating:

- the 2-sided 95% CIs for the difference in log-transformed HI antibody titers against each of the 4 influenza vaccine strains at 28 days after the administration of the seasonal influenza vaccine between the Control and the CoAd group for the standard-dose.

- the 2-sided 95% CIs for the difference in log-transformed S-ELISA titers at 28 days after the administration of Ad26.COV2.S vaccine between the Control and the CoAd group.

For *HI antibody titers* against each of the 4 influenza vaccine strains and for *S-ELISA titers*, an analysis of variance (ANOVA) model will be fitted with the respective titers as dependent variable and group (Control or CoAd), age category (as stratified), previous SARS-CoV-2 vaccination (as collected), and baseline S-ELISA titers as independent variable. The strata will be based on the values in the database for vaccination history (which may differ to the strata as recorded in IWRS).

Based on these ANOVA models, the CIs around the difference will be calculated and will be back transformed (by exponentiation) to CIs around a GMC or GMT ratio (Control group / CoAd group), respectively, and compared to the NI margin of 1.5.

Only if the upper bound of the 2-sided 95% CI for the GMT or GMC ratio (Control group/CoAd group), respectively, of the HI antibody titer for each of the 4 vaccine strains and for S-ELISA lies below 1.5, NI of coadministration versus separate administration will be concluded for both vaccines (seasonal influenza vaccine and Ad26.COV2.S vaccine). If 1 or more confidence limits for the GMC or GMT ratio exceed 1.5 non-inferiority cannot be concluded.

For immunogenicity, baseline is considered as the last assessment pre-vaccination (i.e. it corresponds to Day 1 for CoAd groups or influenza vaccine alone, or to Day 29 for Control groups or Ad26.COV2.S vaccine alone). In a sensitivity analysis, different variances between the groups will be allowed. Therefore, the CIs will be calculated via Welch's ANOVA.

The assessment of the primary endpoints will be performed on individuals who have been previously vaccinated with different types of COVID-19 vaccines. Furthermore, participants may have or not an history of COVID infection. These factors bring a level of variability of immune responses that is unknown.

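### Overall power of at least 90% for all five non-inferiority tests does not follow from the listed sample-size inputs, which give about 88–89% under independence

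*Protocol*

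**What the plan says.** Protocol 9.2 and SAP 3 list the same main inputs:

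- no true effect of co-administration on either response;
- log10 SD of 0.53 for HI titers and 0.50 for S-ELISA;
- a margin of 1.5 and a 2-sided alpha of 5%.

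Both plan about 305 standard-dose participants per group, and the SAP says these "are needed to have 97.45% power to show non-inferiority in HI antibody titers for each influenza vaccine strain". The protocol describes 305 as a figure that already covers losses: "The sample size accounts for exclusions from the per protocol set (see Section 9.3), drop-outs and missing samples". SAP 3 sizes that allowance: "The N margin was" about 10%, or about 30 per group. The synopsis says the primary objective "will be evaluated in approximately 610 participants aged 18 and above who have completed a primary COVID-19 vaccine series".

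Success needs the four HI strains and S-ELISA to pass together. Protocol 9.1 says: "If 1 or more confidence limits for the GMT/GMC ratio exceed 1.5, NI cannot be concluded".

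On that basis Protocol 9.2 says the power for the four strains "as well as NI in S-ELISA at 28 days after the administration of Ad26.COV2.S vaccine is at least 90" percent. The synopsis (Statistical Methods) and SAP 3 repeat the figure. Neither document gives a correlation between endpoints, a covariate-adjusted SD, or separate evaluable numbers for HI and S-ELISA.

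**The concern.** A power described as at least some value is a lower bound. Without a stated correlation, there are two usual ways to get a joint power from marginal powers: multiply them (independence), or subtract the summed failure probabilities from 1 (valid under any dependence). Both should reach 90% if the bound follows from the listed inputs.

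Raising the stated per-strain power to the fourth power gives just over 90%, which leaves almost no room for a fifth test. The figure concerns the trial's only success criterion and appears in three places, so a reader should be able to rebuild it. The issue is whether the stated power is supported, not whether the design is badly underpowered.

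**Working it through.** **Inputs.** From Protocol 9.2 and SAP 3: SD 0.53 (HI) and 0.50 (S-ELISA), true ratio 1, margin log10(1.5) = 0.1761, one-sided 2.5% per test. From SAP 3: 305 per group less about 30 leaves 275 evaluable.

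**Method.** For each endpoint, SE = SD × √(2/n) and the noncentrality is 0.1761/SE. Power comes from the noncentral t with 2n − 2 degrees of freedom. With H the power for one strain and S the power for S-ELISA:

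- all five, independent: H^4 × S
- floor under any dependence: 1 − 4(1 − H) − (1 − S)

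**Step 1: reproduce 97.45%.** At n = 278, SE = 0.53 × √(2/278) = 0.04495 and the noncentrality is 3.917, so H = 97.44%. The stated figure therefore corresponds to about 278 evaluable per group, close to the 275 left by the SAP's allowance. At 305 evaluable, H would be 98.4%, which is not the stated value.

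**Step 2: start from the stated 97.45%.** Four independent strains give 0.9745^4 = 0.9018. To keep 90%, S-ELISA would need 0.90/0.9018 = 99.8% power, which takes about 378 evaluable per group at SD 0.50. What is available:

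| S-ELISA evaluable per group | S-ELISA power | 0.9018 × S-ELISA power |
|---|---|---|
| 275 | 98.47% | 88.8% |
| 278 | 98.56% | 88.9% |
| 305 (no losses) | 99.14% | 89.4% |

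Under independence, the stated per-strain power cannot give 90% overall even if every planned participant supplies an S-ELISA result.

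**Step 3: same evaluable number for every endpoint.**

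| n per group | H | S | Four strains (H^4) | All five, independent | Floor, any dependence |
|---|---|---|---|---|---|
| 275 | 97.31% | 98.47% | 89.7% | 88.3% | 87.7% |
| 278 | 97.44% | 98.56% | 90.2% | 88.9% | 88.3% |
| 305 | 98.37% | 99.14% | 93.6% | 92.8% | 92.6% |

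A normal approximation gives 88.5% and 89.0% in place of 88.3% and 88.9%. By the t calculation, 90% needs 285 evaluable per group under independence, or 288 whatever the dependence.

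**Step 4: what would bring it to 90%.** The values below are assumptions, since the documents give none.

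- *Correlation.* With equal correlation among the strains and S-ELISA independent, 0.3 gives 89.3–89.9% and 0.5 gives 90.3–90.9%. The ranges cover n = 275 to 278 and both the t and normal calculations.
- *Covariates.* Suppose the listed SDs are unadjusted and the model explains the same share of variance in all five endpoints, so that SD becomes SD × √(1 − R²). An R² of 0.03 gives 90.3% at 278, and 0.04 gives 90.3% at 275, under independence. If only S-ELISA benefits, an R² of about 0.3 is needed at 278.
- *Numbers.* HI at 286 with S-ELISA at 278 gives 90.0%, that is, 8 extra evaluable participants per group in the influenza analysis.

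**The case against.** The strongest reply is that 88–89% rests on independence, which the plan never assumes. The four HI titers come from the same people, vaccine and assay, so zero correlation is conservative. A strain correlation of about 0.4 at 278 per group, or 0.3 across all five endpoints, brings power to 90%. The floor under any dependence requires failures that never coincide, which is unlikely here.

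The plan also contains two other routes to 90%. The primary model for every endpoint includes age category, "previous SARS-CoV-2 vaccination (as collected), and baseline S-ELISA titers as independent variable", and a common R² of only 0.03–0.04 is enough. In SAP 4, "PPII set will include participants who have received a complete primary vaccination with an authorized/licensed COVID-19 vaccine as well as" vaccine-naïve participants, whereas the 610 counts only the previously vaccinated, so HI numbers may exceed S-ELISA numbers. Finally, the inputs are approximate: 285 evaluable per group would do, which is 7 more than 278.

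Most of this stands as a reason to think actual power may be 90% or more. It does not rescue the stated bound, because no correlation, R² or naïve count appears in either document. The naïve route is also uncertain: Protocol 9.4.2 and SAP 5.3.2 describe the primary assessment as being in previously vaccinated people, and the S-ELISA set excludes naïve participants. Reading 305 as fully evaluable gives 92.8%, but that contradicts both the 97.45% and the loss allowance.

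**Conclusion.** The concern holds, as a minor point. The listed inputs reproduce 97.45% per strain at about 278 evaluable per group but do not support an overall power of at least 90%. With 275–278 evaluable for every endpoint, joint power is 88.3–88.9% under independence and at least 87.7–88.3% under any dependence. The shortfall is roughly one to two percentage points.

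That the four-strain product lands just above 90% is consistent with S-ELISA having been left out of the calculation, but does not prove it. The result assumes the listed SDs apply to the analysis as fitted, equal evaluable numbers across endpoints, and a true ratio of 1. It shows an unsupported bound; it does not show that true power is below 90%.

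**What to change.** Change the sentence in the protocol synopsis, Protocol 9.2 and SAP 3 in one of two ways.

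1. State overall power as about 88–89%, assuming independent endpoints and about 275–278 evaluable participants per group for each endpoint, and note that it is higher if endpoints are positively correlated or covariates reduce the residual variance.
2. Keep 90% and state what produces it: the assumed correlation, the residual SD after adjustment, or the evaluable number. Give the influenza (PPII) and SARS-CoV-2 (PPSI) numbers separately if they differ.

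The second is preferable if the sponsor has such a basis on file. Either costs one sentence in three places, with no change to enrolment, the decision rule or type I error.
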